8.0 Criteria for Removal from the Study

Toxicity monitoring will be focused on neurological, gastrointestinal, musculoskeletal, hematologic, and dermatologic systems. Toxicity will be graded according to NCI toxicity scale. Patients who have evidence of disease progression will be noted as tumor progression on the date progression is observed. Patients will be seen according to the follow up schedule for toxicity monitoring until death unless they withdraw consent for participation in the study in which case they will be removed from the study. For patients unable to return for follow-up clinic visits due to progressive disease or illness, these patients will be monitored via telephone follow-up until time of death.

9.0 Statistical Considerations

The advantage of stereotactic radiation given in a single session is one of convenience, both for the patient, and for the treatment team, since each treatment can last up to 2 hours. However, single fraction stereotactic body radiotherapy to the spine must be evaluated for safety in terms of avoiding spinal cord myelitis or myelopathy, since there is no opportunity to correct for positioning errors, and once radiation has been delivered, any spinal cord sequelae that occurs is likely to be irreversible. Data from our current protocol for 3 fraction stereotactic radiation to the spine has demonstrated that the 95% confidence interval of the probability of developing paralysis is between 0 and 10% based on the Clopper-Pearson analysis of approximately 70 patients treated so far, and no cases of paralysis have been observed to date. We wish to treat patients in a single fraction with stopping rules such that the trial will halt if the probability of paralysis exceeds 1%.

The statistical characteristics of this trial for single session stereotactic radiation to the spine are described below. The primary issues in the trial are safety (proportion of paralysis) and effectiveness (tumor control, pain relief). The trial is intended to test the safety of giving stereotactic radiation in a single session and to determine tumor control based on spinal MRI. The prevalence and severity of spinal pain at pre-treatment baseline, and during longitudinal follow-up will be measured.

SAFETY

The trial will terminate (and a lower dose studied) if the investigator determines that there is evidence of paralysis (Grade 4 motor neuropathy) caused by radiation myelitis and not by tumor progression or spinal cord compression is at a rate of the treatment is greater than 0.01 (1%).

Sixty patients will be enrolled for the safety portion of the trial. The patients will be regularly monitored through follow-up visits for signs and symptoms of neurological toxicity. The probabilities of such termination as a function of the toxicity probability is shown below.

Design of the Trial

----- High -----			
Num Subj	Cont	Pr Quit	Cum Probability Quit
15.	1.	0.00963	0.00963
30.	1.	0.02652	0.03615
45.	2.	0.00247	0.03861

60. 2. 0.00809 0.04670

Properties of the Design Assuming the Null Hypothesis
(p = 0.0100)

Quit If Evidence That $\Theta > H_0$

Prob Event	Prob Quit	Expected N	Expected N Given Quit
0.0100	0.0467	58.73	32.87

Properties of the Design Assuming Other Values of p

Quit If Evidence That $\Theta > H_0$

Prob Event	Prob Quit	Expected N	Expected N Given Quit
0.0500	0.6381	43.06	33.45
0.1000	0.9566	27.67	26.21
0.1500	0.9969	20.76	20.64
0.2000	0.9998	17.70	17.69

RESPONSE RATE

Assuming that safety concerns are met, the purpose of the trial is to estimate the response (pain relief) rate. All 60 patients entered will be used for this purpose.

Tumor control will be based on spinal MRI showing absence of progression. Actuarial and crude rates of tumor control will be calculated.

Pain relief will be assessed by items on the BPI that measure severity, location, chronicity, and degree of relief due to therapy by demographic data that will track use of narcotic and non-narcotic pain medications. For previously unirradiated patients as are in this trial, 46% of patients should demonstrate complete sensory pain relief and 90% should have some pain relief reported as a decrease in severity rating and use of pain medications and increase in the pain relief rating (Blitzer 1985).

The expected change in these indicators should occur within 1 month from the end of radiation therapy based on experience with 3 fraction SBRT on protocol ID02-446. Forty percent of patients should demonstrate complete sensory pain relief by 6 months from the end of radiation therapy as reported by the same indicators. Duration of sensory pain relief should approach a mean of 24 weeks for those patients reporting some relief and 13 weeks for those patients reporting complete relief. For patients surviving one year or more, 60% should report sustained relief based on results with standard radiation therapy.

Pain, Symptom and Quality of Life Instruments

The MD Anderson Symptom Inventory (MDASI) is a measure of symptom severity and symptom interference while the SF-12v2 Health Survey is a measure of health status. Because changes in symptom severity are usually associated with changes in health status, we are interested in assessing the relationship of symptom severity and symptom interference on health-related functional status of life using the SF12's physical and mental component scores. We will regress the MDASI with the component scores of the SF12 and examine the overlap in variability between the measures.

The "pain worst" item from the BPI will be used as the marker for treatment success or failure. Previous studies have shown that pain severity can be categorized into mild, moderate or severe based on how pain interferes with daily functions (Serlin et al, 1995, Mendoza, et al 2004). We will calculate the proportion of patients who responded to treatment. We expect 80% of patients to respond to declare success. A responder will be defined as a patient whose "pain worst" changed from moderate or severe (5 or greater on the) to none or mild (0-4) at 1 month after enrollment. This range was selected because previous studies have shown that patients who report pain of 5 or greater on this item experience significantly greater pain-related interference with function than those with mild or no pain [Cleeland et al, 1994, Serlin et al, 1995, Wang et al, 1999].

The following are secondary considerations in determining treatment failures and pain relief.

Treatment Failures

All the following are considered treatment failures:

- 1) A pain score greater than 0 that does not change within 8 weeks from start of radiation therapy.
- 2) A 2 point increase in "worst pain score" that is sustained at a higher level in the month following the first day of radiation therapy.
- 3) A pain score that drops by at least 2 points and subsequent sustained rise (on 2 successive questionnaires) of pain score by at least 2 points.

Pain Relief

- 1) Patients experiencing a decrease of 2 points in the worst pain score for 2 consecutive analysis periods will be considered to have "partial pain relief."
- 2) Complete pain relief is defined as an average pain score of 0 for 2 consecutive analysis periods.

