6.0 Evaluation During Study

Patients will be evaluated at 1, 2, 3, and 4, and 8 weeks following completion of radiation therapy by telephone, fax, or mail. Patients will be seen for follow up visits at 3, 6, 9, 12, 18, and 24 months and then every six months thereafter; History, neurological exam, and neurologic function according to the McCormick scale will be assessed. MRI of the spine will be obtained at 3, 6, 9, 12, 18, and 24 months and then every six months thereafter. Included in the appendices, the Brief Pain Inventory (BPI) (Short Form), MD Anderson Symptom Inventory (MDASI) and SF-12v2 Health Survey will be administered at each clinic and telephone follow up. Pain medication requirements will be recorded on the BPI.

The BPI is a 17 item patient self rating scale assessing demographic data, use of medications, as well as sensory, and reactive components of pain (5). Reliability has been demonstrated over short intervals using test retest item correlation; worst pain, r=0.93; usual pain, r=0.78; pain now, r=0.59. The BPI includes items that will address components of sensory pain including severity, location, chronicity and degree of relief due to therapy. The BPI also has items that address reactive pain components including depression, suffering and perceived availability of relief.

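### The paralysis limits are tabulated only at 15, 30, 45 and 60 patients; applying them at each event keeps every stopping probability and treats fewer patients

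*Combined protocol and SAP*

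**What the plan says.** The termination sentence in section 9.0 (Safety) opens "The trial will terminate (and a lower dose studied) if the investigator determines that there is evidence of paralysis (Grade 4 motor neuropathy" and sets the trigger at a rate above 1%. It is not tied to any look. Sixty patients are enrolled, and the section then introduces its design tables: "The probabilities of such termination as a function of the toxicity probability is shown below".

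The design table lists the largest event count at which the trial continues: 1 at 15 patients, 1 at 30, 2 at 45 and 2 at 60. Its last row reads "60. 2. 0.00809 0.04670", so the cumulative probability of quitting at a true rate of 1% is 0.0467. A further table, headed "Properties of the Design Assuming Other Values of p", gives the probability of quitting and expected N at 5, 10, 15 and 20%.

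Several provisions can act between looks. Section 10.0 sends Grade 3 and 4 toxicity to the IRB. Section 11.0 has each new serious event reviewed alongside the earlier ones and allows immediate suspension on a monitoring report. None of them states a count.

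Follow-up is long. Section 6.0 says "Patients will be evaluated at 1, 2, 3, and 4, and 8 weeks following completion of radiation therapy by telephone, fax, or mail", with clinic visits from 3 months onward, and section 8.0 says "Patients will be seen according to the follow up schedule for toxicity monitoring until death". Paralysis may therefore be found well after the patient was treated.

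**The concern.** Section 9.0 explains why this event matters: after a single fraction, "any spinal cord sequelae that occurs is likely to be irreversible". Suppose the second radiation-induced paralysis occurs in patient 17. The limit for the 30-patient look has then been passed and no later result can reverse it, yet the table does not act until patient 30. The reviewers who receive the event report have no stated number to apply. Patients treated between the event and the look are exposed with no gain in information about whether the rule will be met.

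The second gap is the counting rule. If patient 28 was treated early but the paralysis is recognised when 36 are enrolled, the plan does not say whether the limit for the first 30 or the limit for 31 to 60 applies. That choice decides whether the tabulated stopping probabilities still hold when events are found late.

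**Working it through.** **Inputs (section 9.0).** Maximum N = 60. Quit at 2 or more events at n = 15 or 30, and at 3 or more at n = 45 or 60. This takes the printed count as the largest at which the trial continues. The alternative reading, quitting at the printed count, gives a probability of 0.287 at 1% and does not match the table.

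**Step 1: reproduce the table.** An exact binomial recursion with checks at the four looks gives, at p = 0.01, quitting probabilities of 0.00963, 0.02652, 0.00247 and 0.00809, total 0.0467, and expected N 58.73. All match. Every probability and expected N at 5 to 20% also matches. The one discrepancy is trivial: expected N given quitting at 1% is 32.90 against 32.87 printed.

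At p = 0.05 the probabilities at the four looks are 0.17095, 0.27551, 0.06571 and 0.12591, and 0.36192 of trials never quit. So E[N] = 15(0.17095) + 30(0.27551) + 45(0.06571) + 60(0.12591 + 0.36192) = 43.06, the printed value. The printed expected N therefore assumes stopping at the four looks only.

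**Step 2: why the stopping probability does not depend on when one looks.** Let X be the events among patients 1–30 and Y those among patients 31–60. The trial runs to the end without quitting exactly when X ≤ 1 and X + Y ≤ 2:

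Pr(quit) = 1 − [P(X=0)·P(Y≤2) + P(X=1)·P(Y≤1)]

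- p = 0.01: 1 − [0.73970 × 0.99668 + 0.22415 × 0.96385] = 0.0467
- p = 0.05: 1 − [0.21464 × 0.81218 + 0.33890 × 0.55354] = 0.6381

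The expression does not involve the timing of checks.

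**Step 3: apply the same limits after every patient** (2nd event up to patient 30, 3rd event in patients 31–60), with outcomes known at once:

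| True rate | Pr(quit), both schemes | E[N], four looks | E[N], each event | Saving |
|---|---|---|---|---|
| 1% | 0.0467 | 58.73 | 58.46 | 0.3 |
| 2% | 0.1727 | 55.65 | 54.63 | 1.0 |
| 5% | 0.6381 | 43.06 | 39.08 | 4.0 |
| 10% | 0.9566 | 27.67 | 21.25 | 6.4 |
| 15% | 0.9969 | 20.76 | 13.63 | 7.1 |
| 20% | 0.9998 | 17.70 | 10.05 | 7.6 |

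At 5%, 92% of the trials that stop cross the limit between looks. Those trials treat 6.8 more patients on average before the next look. Over all stopping trials the figure is 33.45 − 27.21 = 6.2.

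**Step 4: late detection.** The safety section gives no accrual rate or assessment window, so the lag is an assumption: the latest 6, 9 or 15 patients are not yet assessable, and the count is complete at the end. At a true rate of 5%:

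| Lag (patients) | E[N] by treatment order: four looks / each event | Saving | Saving, counted by number enrolled | Pr(quit), treatment order | Pr(quit), number enrolled |
|---|---|---|---|---|---|
| 6 | 46.8 / 42.7 | 4.0 | 3.3 | 0.638 | 0.618 |
| 9 | 48.4 / 44.4 | 4.0 | 3.1 | 0.638 | 0.609 |
| 15 | 50.7 / 47.6 | 3.1 | 2.4 | 0.638 | 0.596 |

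Savings are taken before rounding. At a lag of 30 the saving is about 2.8 by treatment order and about 1.1 by number enrolled. At a true rate of 1%, Pr(quit) is 0.0467 by treatment order, and 0.038, 0.034 or 0.028 by number enrolled at lags of 6, 9 and 15.

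**The case against.** The strongest reply is that four looks make an ordinary grouped design with correctly stated properties, and that nobody would in practice wait for patient 30 after a second radiation-induced paralysis. The termination sentence is not tied to a look, two events in at most 30 patients is an observed rate of at least 2/30 = 6.7%, and the IRB sees serious events as they occur. A reader of the table can also infer that a second event at patient 17 already exceeds the next limit. On this view the tabulated saving is a worst case.

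Much of this stands. The table contains no error, and the saving assumes strict adherence to the looks. But the termination sentence cannot stand in for a count: read as an observed proportion, it would be met by one event in 60 (1.7%), where the table continues. The IRB provisions supply a route for acting but no number.

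Three further points are fair.

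- The gain is negligible near 1%.
- The table prints no limit for patients 31 to 44, so the 3rd-event limit there is a choice. It is the one that preserves the plan's own probabilities; carrying the 2nd-event limit forward to patient 44 would raise Pr(quit) to 0.0752 at 1% and 0.7033 at 5%.
- Restoring Pr(quit) under delay does not mean all those trials stop early. With a lag of 15 at 5%, counted by treatment order, only about 0.45 (four looks) or 0.50 (each event) stop before all 60 are treated.

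**Conclusion.** The point holds as an inexpensive improvement to a valid design. With immediate detection, the plan's own limits applied at each event give identical stopping probabilities and save about 4 patients on average at a true rate of 5% and 6.4 at 10%. Both rates lie within the 0 to 10% interval that section 9.0 quotes from the earlier protocol. The no-lag results are exact. The lagged results rest on assumed delays; the saving shrinks as the delay grows but was still positive at a lag of 30 patients.

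The counting rule is a separate ambiguity with its own effect: at lags of 6 to 15 patients, counting by number enrolled lowers Pr(quit) at 5% from 0.638 to between 0.618 and 0.596. Counting by treatment order returns both the 5% and the 1% figures to their tabulated values. At 1% that means a higher chance of stopping, 0.0467, than under the other rule.

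**What to change.** Add two statements to section 9.0 (Safety):

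1. The existing limits apply at each confirmed qualifying event: the rule is met by a 2nd event among the first 30 treated patients or a 3rd among all 60. The 2nd-event limit should be confined explicitly to the first 30.
2. Events are assigned by order of treatment, whenever they are detected.

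Then recalculate the two expected-N columns. With immediate detection, overall expected N becomes 58.46, 39.08, 21.25, 13.63 and 10.05 at 1, 5, 10, 15 and 20%. Expected N given quitting becomes 27.1, 27.2, 19.5, 13.5 and 10.0.

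The overall Pr(quit) figures and the sample size do not change. The cost is minor wording, the two columns, and event-by-event checking through the existing serious-event route to the IRB.

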3.0 Patient Eligibility

Inclusion Criteria:

- 1) Radiographically documented spine or paraspinal metastasis demonstrated on spine MRI within 4 weeks of registration
- 2) Maximum of 2 metastatic sites in the spine to be irradiated in single session
- 3) Informed consent for irradiation of spinal or para-spinal tumor (s)
- 4) Diagnosis of cancer including but not limited to lung (non-small cell and small cell), breast, prostate, renal cell, melanoma, gastrointestinal, and germ cell tumors, unknown primary tumors
- 5) Karnofsky performance status of at least 40 (ie not requiring active hospitalization)

Exclusion Criteria:

- 1) Worsening neurological status due to radiographic evidence of spinal cord compression requiring immediate surgical decompression or emergent conventional external radiation therapy.
- 2) Delay in initiation of radiation treatment would be potentially detrimental to neurological outcome
- 3) Prior irradiation to current site of interest in the spine
- 4) Spinal metastasis in the cervical spine are not eligible for treatment
- 5) Unstable spine requiring surgical stabilization.
- 6) Sites outside the spine (eg. lung, liver) are not eligible for treatment
- 7) Patients currently receiving, or who have received chemotherapy within 30 days are not eligible
- 8) Inability to tolerate lying flat on treatment couch for greater than 30 minutes.
- 9) Patient with multiple myeloma
- 10) Patients unable to undergo MRI of the spine
- 11) Patients with pacemakers

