7.0 Criteria for Response

Pain, Symptom and Quality of Life Instruments

Frequency and duration of complete pain relief will be the primary endpoint for efficacy of the study. The validated Brief Pain Inventory (BPI), MD Anderson Symptom Inventory (MDASI), and SF-12v2 Health Survey will be used to assess changes in these indicators compared to pre-treatment baseline. Response will be determined by follow-up questionnaires. Time to maximal pain relief will be the time from the first day of irradiation until the lowest pain score for average pain after radiotherapy. The "worst pain score" from BPI will be used as the marker for treatment success or failure.

Treatment Failures

All the following are considered treatment failures:

- 1) A pain score greater than 0 that does not change within 8 weeks from start of radiation therapy.
- 2) A 2 point increase in "worst pain score" that is sustained at a higher level in the month following the first day of radiation therapy.
- 3) A pain score that drops by at least 2 points and subsequent sustained rise (on 2 successive questionnaires) of pain score by at least 2 points.

Pain Relief

- 1) Patients experiencing a decrease of 2 points in the worst pain score for 2 consecutive analysis periods will be considered to have "partial pain relief."
- 2) Complete pain relief is defined as an average pain score of 0 for 2 consecutive analysis periods.

Radiographic Assessments.

MRI of the spine will be performed according to standard of care. These data will be collected on treated lesions and will be classified as progressive defined as larger, stable defined as radiographically unchanged, or smaller.

The date of radiological progression will be recorded. Progression free survival based on time to event curves will be calculated.

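### The 80% pain-response criterion has no stated denominator other than all 60 patients, yet patients entering with worst pain of 0 to 4 cannot meet the responder definition

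*Combined protocol and SAP*

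**What the plan says.** Section 9.0 (Statistical Considerations) sets the sample size under Safety: "Sixty patients will be enrolled for the safety portion of the trial". Under Response Rate, once safety is satisfied, the aim is to estimate the pain-relief response rate, and "All 60 patients entered will be used for this purpose".

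The criterion itself is further on in section 9.0, under Pain, Symptom and Quality of Life Instruments: "We will calculate the proportion of patients who responded to treatment", followed by "We expect 80% of patients to respond to declare success". A responder is a patient whose BPI worst pain "changed from moderate or severe (5 or greater on the) to none or mild (0-4) at 1 month after enrollment". The text explains why 5 was chosen as the cut. It does not say that only patients at or above 5 are counted.

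Section 3.0 (Patient Eligibility) bases entry on imaging: "Radiographically documented spine or paraspinal metastasis demonstrated on spine MRI within 4 weeks of registration". None of its inclusion or exclusion criteria mentions pain. Section 9.0 treats baseline pain as something to be observed: "The prevalence and severity of spinal pain at pre-treatment baseline, and during longitudinal follow-up will be measured".

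**The concern.** The responder definition needs a starting score of 5 or more, but entry to the trial does not. A patient who enrols with worst pain of 0 to 4 can never be a responder, whatever the treatment does. If that patient is in the denominator, the estimated rate falls for a reason unrelated to treatment.

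The estimate and the 80% statement would then depend on who enrols as well as on how well the treatment works. Two cohorts with the same benefit among patients in moderate or severe pain could give different rates, and one could miss 80% only because it enrolled more patients with mild pain. If the denominator is instead left to the analyst, it may be chosen after the data are seen, and the choice can decide whether 80% is met.

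**Working it through.** **Inputs from the plan (section 9.0).** N = 60; responder means worst pain going from 5 or more to 0-4 at 1 month; 80% of patients for success. The plan gives no null rate, significance level, power or precision for the 80%, so there is no derivation to reproduce. The 60 comes from the safety design.

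**Assumed inputs.** q, the share entering at 0-4, is not in the documents; 0 to 20% is used (0 to 12 of 60). p, the true response rate among patients starting at 5 or more, is set to 80% (the plan's expectation) and to 90% (an illustrative higher rate).

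**Expected observed rate over all 60 = (1 - q) × p.**

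| q | p = 80% | p = 90% |
|---|---|---|
| 5% | 0.95 × 0.80 = 76% | 0.95 × 0.90 = 85.5% |
| 10% | 0.90 × 0.80 = 72% | 0.90 × 0.90 = 81% |
| 15% | 0.85 × 0.80 = 68% | 0.85 × 0.90 = 76.5% |
| 20% | 0.80 × 0.80 = 64% | 0.80 × 0.90 = 72% |

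**Ceiling.** 80% of 60 is 48 responders. With 12 patients at 0-4, 48 can respond, so every one must (48/48). With 13, at most 47 can, and 47/60 = 78.3%. So 80% cannot be reached with 13 or more.

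**Chance of reaching 48/60 (illustration only, reading 80% as a cut on the observed rate).** Two models are shown. In the first, the number at 0-4 is exactly 60q, and the chance is P(X ≥ 48) for X ~ Bin(60(1 - q), p). In the second, q is each patient's probability of entering at 0-4, and X ~ Bin(60, (1 - q)p).

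| q | p = 90%, exact number at 0-4 | p = 90%, q as enrolment probability |
|---|---|---|
| 0 | 0.99 (n = 60) | 0.99 |
| 10% | 0.71 (n = 54) | 0.65 (60 patients, 0.81 each) |
| 20% | 0.006 (n = 48) | 0.11 (60 patients, 0.72 each) |

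At p = 80% under the exact-number model, the chance is 0.58 at q = 0, 0.065 with 6 patients at 0-4, and below 0.0001 with 12.

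**Restricted denominator, same range of q.** The chance of observing at least 80% among n patients starting at 5 or more is P(X ≥ 0.8n, rounded up), X ~ Bin(n, p).

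| n (needed) | p = 90% | p = 80% |
|---|---|---|
| 60 (48) | 0.994 | 0.576 |
| 54 (44) | 0.983 | 0.473 |
| 48 (39) | 0.981 | 0.500 |

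The steep fall with q disappears. A true 80% still passes only about half the time, as expected when the cut sits at the true rate.

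**The case against.** The strongest reply is that the sentence about all 60 patients does not set this denominator. It opens the efficacy part directly after the safety part fixes 60 patients, and can naturally be read as saying that the safety cohort also serves for efficacy, with no separate accrual. The responder definition comes later and does not refer back to the 60. Its wording starts from moderate or severe pain, so an analyst could reasonably count only patients who began there. Section 9.0 also uses subsets for other pain quantities, such as duration among patients with some relief.

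This stands in part. A reader might infer that the plan unmistakably makes patients with mild pain automatic failures; the documents do not support that much certainty. But the alternative reading leaves no stated denominator, since the two sentences on the proportion and the 80% refer to patients without qualification. The text needs the same amendment either way.

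It is also fair that the 80% is worded as an expectation, with no test attached, and that the stated aim is estimation. The cut at 48/60 is therefore a reading, and the pass probabilities only illustrate it. The most striking of them, 0.006, depends on fixing exactly 12 patients at 0-4; with q = 20% as an enrolment probability it is 0.11. The dilution factor (1 - q) needs neither the cut nor that choice.

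**Conclusion.** The concern holds in this form: applied with the only denominator the plan states, the 80% criterion counts patients entering at 0-4 as non-responders regardless of treatment, and nothing in eligibility keeps them out. The expected rate is then multiplied by (1 - q). A true 80% reads as 72% at q = 10% and 64% at q = 20%, and 80% is unattainable once 13 of 60 enter at 0-4.

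The size rests wholly on q, which is assumed; if every patient enters at 5 or more, there is no effect. The documents therefore do not show that the trial will miss 80%, only that the result can turn on case mix.

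A reader might also extend the point to complete pain relief, of which section 7.0 says "Frequency and duration of complete pain relief will be the primary endpoint for efficacy of the study". That definition has no baseline condition either, but the direction of any distortion is unresolved: patients pain-free at entry would lower the rate if kept only in the denominator, and raise it if the definition is applied literally and they stay at 0. The 46% complete-relief figure in section 9.0 is attributed to a cited source, and nothing shows that it applies to this plan's definition over two consecutive periods. No size can be put on that extension, and it is not part of this finding.

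**What to change.** In section 9.0, state that the 80% criterion applies to entered patients with baseline BPI worst pain of 5 or more. Report that n and the response rate with an exact 95% confidence interval. Report patients with baseline worst pain of 0-4 separately, for example as the proportion staying at 4 or below. Amend the sentence about all 60 patients so that it no longer sets this denominator; the 60 for safety is unaffected. The same edit should say how a missing 1-month score is counted, or the denominator stays partly open.

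This is a text change. Section 5.0 already collects the BPI at baseline, so no new data are needed. The cost is precision: the efficacy n becomes smaller and is not known in advance. At an observed 80%, the exact (Clopper-Pearson) 95% interval is 68-89% for 48/60, 64-91% for 32/40 and 61-92% for 24/30. As the last table in the working shows, restriction removes the dependence on case mix but does not make a true 80% likely to pass.

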5.0 Pretreatment evaluation

- 1) Patients will undergo a history and neurological exam. Neurologic function will be graded from 1 to 4 according to the McCormick classification scheme.
- 2) MRI of the spine must be performed within 1 month of registration.
- 3) A pretreatment CT scan will be obtained for treatment planning.
- 4) The SF-12v2 Health Survey, the M.D. Anderson Symptom Inventory (MDASI) and the Brief Pain Inventory (BPI Short Form), which includes assessment of pain medications will be administered for baseline assessment within 1 week of registration.
- 5) At the time of enrollment, patients will be noted to either have hepatic metastases present or absent.
- 6) Based on the radiation treatment plan, the gross tumor volume (GTV) representing the spinal or paraspinal metastasis, the clinical target volume (CTV) representing the GTV and the entire vertebral body for spinal metastases will be recorded.

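### The MDASI and SF-12 regression has no repeated-measures structure and does not separate within-patient change from differences between patients

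*Combined protocol and SAP*

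**What the plan says.** The analysis is in Section 9.0, under Pain, Symptom and Quality of Life Instruments.

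- **Rationale:** "Because changes in symptom severity are usually associated with changes in health status".
- **Question:** "we are interested in assessing the relationship of symptom severity and symptom interference on health-related functional status of life", using the SF-12 physical and mental component scores.
- **Method, in full:** "We will regress the MDASI with the component scores of the SF12 and examine the overlap in variability between the measures".

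The data come from repeated administrations.

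- **Baseline (Section 5.0):** the questionnaires "will be administered for baseline assessment within 1 week of registration".
- **Early follow-up (Section 6.0):** "Patients will be evaluated at 1, 2, 3, and 4, and 8 weeks following completion of radiation therapy by telephone, fax, or mail".
- **Later follow-up (Section 6.0):** "Patients will be seen for follow up visits at 3, 6, 9, 12, 18, and 24 months and then every six months thereafter".
- **Instruments at follow-up (Section 6.0):** BPI, MDASI and SF-12v2 "will be administered at each clinic and telephone follow up".

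Section 7.0 adds that the three instruments "will be used to assess changes in these indicators compared to pre-treatment baseline". No model for change in MDASI or SF-12 scores appears there or in Section 9.0, so the regression is the only model stated for either instrument.

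**The concern.** The sentence leaves open which visits enter, whether they are pooled, how correlation between records from one patient is handled, whether levels or changes are modelled, and which MDASI score is used. The direction is also unclear: the question suggests SF-12 as the outcome, while the method sentence can be read with MDASI as the outcome.

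These choices decide what the result means. Pooling all records as if independent would overstate precision. It would also blend two associations: whether patients with more symptoms have worse health status than other patients, and whether a given patient's health status moves when that patient's symptoms move. The rationale concerns the second. At stake is how a descriptive secondary result is interpreted, not the safety rule or the pain response.

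**Working it through.** The plan attaches no sample size, correlation, significance level or expected R-squared to this regression, so there is no stated figure to reproduce.

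**Inputs from the documents**
- Patients: 60 (Section 9.0).
- Assessments through 24 months: 1 baseline + 5 remote (weeks 1, 2, 3, 4, 8) + 6 clinic (months 3, 6, 9, 12, 18, 24) = 12. This counts fax and mail contacts as questionnaire contacts and leaves out the six-monthly visits after month 24.
- Records: at most 60 × 12 = 720.

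**Assumed inputs (the documents give none)**
- Intra-patient correlation (ICC) of 0.3, 0.5 or 0.7, the same for predictor and residual.
- 6 completed visits as an alternative, because patients may enter at Karnofsky 40 and Section 8.0 foresees patients unable to return.

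**Step 1: standard errors if visits are pooled**

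For a pooled slope with m visits per patient, the design effect is DEFF = 1 + (m − 1) × ICC_x × ICC_e. The ordinary standard error is too small by a factor of √DEFF.

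| Visits | ICC | DEFF | √DEFF |
|---|---|---|---|
| 12 | 0.3 | 1 + 11 × 0.09 = 1.99 | 1.41 |
| 12 | 0.5 | 1 + 11 × 0.25 = 3.75 | 1.94 |
| 12 | 0.7 | 1 + 11 × 0.49 = 6.39 | 2.53 |
| 6 | 0.3 | 1 + 5 × 0.09 = 1.45 | 1.20 |
| 6 | 0.5 | 1 + 5 × 0.25 = 2.25 | 1.50 |
| 6 | 0.7 | 1 + 5 × 0.49 = 3.45 | 1.86 |

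At 12 visits, the 720 records carry the information of about 720/1.99 = 362, 720/3.75 = 192 or 720/6.39 = 113 independent ones. Simulation with no true association (60 patients, 4,000 runs per setting) gave factors of 1.41, 1.93 and 2.51 at 12 visits, and 1.19, 1.51 and 1.86 at 6.

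If a test at nominal 5% were reported, the simulated type I error would be:

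| Analysis | Type I error |
|---|---|
| Pooled, 12 visits, ordinary standard errors | 17% to 44% |
| Pooled, 6 visits, ordinary standard errors | 10% to 30% |
| Pooled, 12 visits, clustered by patient | 5.2% to 6.0% |
| Pooled, 6 visits, clustered by patient | 5.2% to 6.4% |
| One visit, no correction | 4.8% to 5.4% |

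**Step 2: the overlap itself**

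Suppose half of each score's variance lies between patients, with a between-patient correlation of 0.8 and a within-patient correlation of 0.3 (all assumed). The pooled correlation is 0.5 × 0.8 + 0.5 × 0.3 = 0.55, so the pooled R-squared is 0.55² = 0.30. The between-patient value is 0.8² = 0.64 and the within-patient value is 0.3² = 0.09. The pooled figure matches neither.

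Slopes behave the same way. With assumed slopes of 0.8 between and 0.3 within, the simulated pooled slope averaged 0.45, 0.55 and 0.64 as the predictor's ICC rose from 0.3 to 0.7. A regression of change on change recovered about 0.30, the within-patient value.

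**The case against.** The strongest reply is that the sentence is under-specified rather than wrong. A reader might infer that the plan commits to an ordinary pooled regression, so that its standard errors must be wrong. The documents do not support that: Section 9.0 never says that visits are pooled or treated as independent. A regression at one visit has valid standard errors and answers the relationship question as worded. A change-score regression, such as month 1 minus baseline, also uses one record per patient, fits the use of the instruments in Section 7.0, and does address change.

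A reader might also infer that the stated question is about change. In Section 9.0 change is the rationale; the question is the relationship between symptoms and functional status.

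The promised output is overlap in variability, with no test or interval, and the plan already expects the measures to be associated. False-positive rates under no association are therefore not a measure of harm to this plan. Nor does objective 1.1, which is to document symptoms and quality of life before and after treatment, depend on this regression.

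All of this stands, and it limits the point. It does not remove it. The plan chooses none of the valid options. A single-visit analysis uses one of about 12 assessments and a change-score analysis uses two. The mixing in Step 2 affects a purely descriptive R-squared as much as a test.

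**Conclusion.** The point holds as a minor one. The only model stated for MDASI and SF-12 ignores the structure of the data it will be applied to and leaves the choice of association open.

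If visits are pooled with ordinary standard errors, these are too small by a factor of about 1.4 to 2.5 with 12 visits, or 1.2 to 1.9 with 6 completed visits. The pooled overlap would describe neither patients compared with each other nor patients compared with themselves. Both statements are conditional on pooling. The sizes rest on assumed correlations of 0.3 to 0.7, equal in predictor and residual, and on equal numbers of visits per patient. The R-squared and slope illustrations rest on further assumed values.

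It would go too far to conclude that the analysis will be wrong, or that safety, pain response or tumor control results are affected.

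**What to change.** Replace the method sentence in Section 9.0 with text such as:

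> As an exploratory analysis, each SF-12 component score will be modelled on MDASI severity and MDASI interference in a linear mixed model using all assessments, with a random patient intercept and assessment time as a factor. Each MDASI score will be split into the patient's mean and the deviation from that mean at each assessment. Between-patient and within-patient slopes will be reported with 95% confidence intervals, together with the share of between-patient and of within-patient SF-12 variance that each explains.

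This fixes the direction, the visits and the unit of analysis. It keeps the planned overlap in variability, reported separately for each level. The within-patient slope speaks to the rationale about change, and the between-patient slope to the relationship as worded. The section should also define the two MDASI scores, for example as means of the 13 core symptom items and the 6 interference items described in Section 6.0.

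An acceptable alternative is a regression on the same split terms and assessment time with standard errors clustered by patient. Clustering without the split corrects the precision but still blends the two associations.

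The cost is a change of analysis wording and a slightly more complex model. No new data, visits or patients are needed.
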